### 7.2 SAFETY AND TOLERABILITY VARIABLES

Safety and tolerability will include Adverse Events, physical examination, body weight, vital signs and compliance.

- Adverse events will be recorded throughout the study.
- Physical examination including neck exam, cardiac exam and respiratory exam will be performed at screening and final visits. Body weight will also be recorded at screening, baseline, and final visit.

- Vital signs including heart rate, systolic and diastolic blood pressure will be performed at screening and final visits.
- Patients' compliance with Tirosint® and with the prescribed treatments (levothyroxine as per prescription during the run-in and PPI during the run-in and throughout the whole treatment period) will be assessed by visit based on data reported in the Subject's Diary; Tirosint® compliance will also be assessed by visit based on the Drug Administration.

### 7.3 CONCOMITANT MEDICATIONS

Prior and concomitant medications will be summarized by Anatomical Therapeutic Chemical (ATC) level 2 and Preferred Term (PT) assigned from the WHO drug terms and procedures dictionary for treatments and surgical and medical procedures, showing the number and percentage of subjects from the Safety Population taking each medication. Prior and concomitant LT4/PPI treatments will be summarized separately.

### 7.4 LABORATORY DATA

Laboratory data will include:

- blood sampling for thyroid function tests: TSH, FT4, TT4, FT3, TT3;
- serum laboratory tests: CPK, SHBG, ferritin, ACE, and lipid panel (TC, HDL-C, LDL-C, VLDL-C, TG);

## 8 HANDLING OF MISSING AND INCOMPLETE DATA

Cases of withdrawal from the study, for any reasons, after inclusion will not be replaced. However, the withdrawn cases will be analyzed in the ITT analysis.

TSH, FT4, TT4, FT3, TT3, CPK, SHBG, ferritin, ACE level, and lipid panel (TC, HDL-C, LDL-C, VLDL-C, TG) values recorded after changes in LT4 dose will not be considered for the statistical analysis.

For analyses that require complete patient data, missing values during the treatment period will be replaced, for all primary and secondary variables, with the Last Observation Carried Forward (LOCF) technique. Imputed values will be included in the analysis set(s), but will not change the original clinical database.

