***Visit 3 - Day 42±7 (Interim visit)***

Halfway through the treatment period (i.e. 35-49 days after V2), the patients will report to the clinical center in the morning, holding their daily dose of levothyroxine and bringing with them their diary as well as the unused, used and partially used boxes of Tirosint, and the box/bottle of the PPI, and will undergo:

- adverse events (AEs) and concomitant medications;
- blood sampling for thyroid function tests (TSH, FT4, FT3, TT3) for safety check;
- Tirosint® capsules return and count to check compliance;
- diary collection and check to verify compliance with LT4 and PPI;
- Tirosint® dispensing;
- diary dispensing;
- remind the patient how to complete the diary and how to comply with the study requirements (i.e. drugs intake, study restrictions, etc.).

The new onset or the worsening of clinical signs/symptoms of hypothyroidism or hyperthyroidism (e.g. palpitations) reported by the patient, if clinically significant, will have to be recorded as adverse events.

Any changes in the concomitant medications, including the PPI product and/or dose will be recorded in the CRF.

If the subject brings it, the PPI box/bottle will be checked to verify changes from the previous visit.

All the used boxes of Tirosint® will be collected by the Investigator, pills will be counted for check of compliance and drug accountability, and the boxes will be stored by the Investigator or Pharmacist separately from unused supplies. Leftover pills cannot be re-dispensed.

Patients will be dispensed sufficient amount of Tirosint® capsules for treatment up to Visit 4.

The patients will be asked to take their morning LT4 dose only after blood sampling and will continue taking the study medications at the prescribed dose.

The date of Visit 4 will be scheduled and patients will be asked to come to the clinical center for the next visit, fasting and holding their morning dose of LT4, and bringing with them their diary, the box/bottle of the PPI that they are on therapy with and the used, partially used, and unused boxes of Tirosint®.

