#### *Study discontinuation*

If a patient drops out of the study or in case of study discontinuation (i.e. after inclusion in the Tirosint® treatment phase), the Investigator will attempt to perform a Final Visit, including at least the following assessments for safety purposes:

- adverse events (AEs) and concomitant medications;
- general physical examination (including neck exam, cardiac exam, and respiratory exam);
- body weight (BW);
- vital signs (BP, HR);
- blood sampling for thyroid function tests (TSH, FT4, TT4, TT3, FT3);
- serum laboratory tests: CPK, SHBG, ferritin, ACE, and lipid panel (TC, HDL-C, LDL-C, VLDL-C, TG);
- Tirosint® capsules return and count to check compliance;
- diary collection and check to verify compliance with LT4 and PPI.

If the subject brings it, the PPI box/bottle will be checked to verify changes from the previous visit.

The Investigator will fill in a Study Termination Form in the CRF to explain the reason for study discontinuation.

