### *11.3.3 Missing data*

Cases of withdrawal from the study, for any reasons, after inclusion will not be replaced. However, the withdrawn cases will be analyzed in the ITT analysis.

TSH, FT4, TT4, FT3, TT3, CPK, SHBG, ferritin, ACE level, and lipid panel values recorded after changes in LT4 dose will not be considered for the statistical analysis.

For analyses that require complete patient data, missing values during the treatment period will be replaced, for all primary and secondary variables, with the Last Observation Carried Forward (LOCF) technique. Imputed values will be included in the analysis set(s), but will not change the original clinical database. Sensitivity analyses based on other imputation methods (e.g. Basal Observation Carried Forward [BOCF], maximum-likelihood based method or others) may also be conducted, and will be fully described in the Statistical Analysis Plan.

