#### 7.1.2 Secondary efficacy variables

The secondary efficacy variables are the serum levels of FT4, TT4, FT3, TT3, CPK, SHBG, ferritin, ACE level, and lipid panel; and the LT4 dose adjustment.

Serum levels of FT4, FT3 and TT3 will be measured at screening visit(s), at baseline, halfway through the treatment period and at the final visit. In addition, serum levels of TT4, CPK, SHBG, ferritin, ACE level, and lipid panel (TC, HDL-C, LDL-C, VLDL-C, TG) will be measured at baseline and at the end of the 12-week treatment period (Final visit).

The change in serum levels of TSH, FT4, FT3, TT3 at Visit 3 vs baseline will also be analysed as secondary efficacy endpoint.

The serum levels of TSH, FT4, TT4, FT3, TT3, CPK, SHBG, ferritin, ACE level, and lipid panel recorded after changes in LT4 dose will not be considered for the analysis.

LT4 dose adjustment will be evaluated both in terms of number of patients requiring changes in daily dose during the treatment period and as mean change in daily LT4 dose at the end of the treatment period versus baseline.

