Changes in mean LT4 daily dose/kg at the end of the treatment period versus baseline will be analyzed by a mixed model ANCOVA repeated measures model with LT4 daily dose/kg at each time point as dependent variable. Unstructured covariance structure will be used (If a different type of covariance structure will be used details will be provided).

Normal distribution for the LT4 daily dose/kg data will be tested with Shapiro Wilks.

If LT4 daily dose/kg data results not to be distributed as a normal distribution the following methods will be applied:

- Data will be log transformed and analyzed with the ANCOVA repeated measures model described above.

The secondary efficacy analysis will be performed on data with missing values replaced with LOCF method and on original data (values recorded after changes in LT4 dose will not be considered in either case).

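### For secondary variables with no scheduled sample between baseline and the analysed visit, LOCF usually carries the tablet baseline forward, so the imputed run understates both the change and its uncertainty

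*SAP*

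**What the plan says.** SAP 8 provides that, for analyses needing complete data, "missing values during the treatment period will be replaced, for all primary and secondary variables, with the Last Observation Carried Forward (LOCF) technique". Protocol 11.3.3 has the same rule. SAP 9.4.2 then has the secondary analysis done "on data with missing values replaced with LOCF method and on original data", with values after an LT4 dose change left out of both. It does not say which of the two leads.

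The measurement schedule differs by variable. SAP 7.1.2 states that TT4, CPK, SHBG, ferritin, ACE and the "lipid panel (TC, HDL-C, LDL-C, VLDL-C, TG) will be measured at baseline and at the end of the 12-week treatment period (Final visit". Protocol 7.3 limits the Visit 3 draw to "blood sampling for thyroid function tests (TSH, FT4, FT3, TT3) for safety check".

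Three further provisions bear on what can be carried forward:

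- Protocol 6.2 keeps a patient in the study after a dose adjustment at a control visit, while SAP 8 discards the values that follow.
- Protocol 7.4 (Study discontinuation) says that after a drop-out "the Investigator will attempt to perform a Final Visit, including at least the following assessments for safety purposes". The list includes "blood sampling for thyroid function tests (TSH, FT4, TT4, TT3, FT3" and all the serum tests named above. Protocol 7.6 also allows unscheduled visits.
- Protocol 11.3.3 names an alternative: "Sensitivity analyses based on other imputation methods (e.g. Basal Observation Carried Forward [BOCF". It is optional there, and the SAP does not take it up.

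**The concern.** LOCF is normally defended as carrying a patient's latest value on treatment. For ten secondary variables (TT4, CPK, SHBG, ferritin, ACE and five lipids) the schedule provides no such value before Visit 4. For TSH, FT4, FT3 and TT3 as Visit 3 endpoints it provides none before Visit 3. On the regular schedule the last observation is therefore the Visit 2 value on tablets, and LOCF becomes baseline carried forward, which the protocol lists as a different method.

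The patients most exposed are those whose dose was adjusted at or after Visit 3. They stay in the study, their Visit 4 value is discarded, and they enter the imputed run with no biochemical change on capsules, although their thyroid status had called for an adjustment. At stake is the biochemical part of the secondary objective: in one of two equally ranked runs, the estimates would be pulled towards zero with intervals that are too tight.

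**Working it through.** **The plan's own figure.** Protocol 11.3.1 gives 48 patients, a TSH difference of 0.7, SD of differences 1.9, a paired t-test and two-sided 0.05. The noncentral t with 47 degrees of freedom and noncentrality (0.7/1.9)×√48 gives 70.5% power against the stated 70%. Allowing for 20% loss, 48/(1 − 0.20) = 60. Both figures reproduce.

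**Scheduled on-treatment values before the analysed visit.**

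- TSH, FT4, FT3, TT3 at Visit 4: one (Visit 3).
- TT4, CPK, SHBG, ferritin, ACE, lipids at Visit 4: none.
- TSH, FT4, FT3, TT3 at Visit 3: none.

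With none, the imputed change is baseline minus baseline = 0, and also 0 on the log scale.

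**Effect on the estimate.** Let m be the share of patients given a zero, d the true change in SD units, and N the number analysed. Values are taken as missing at random, and change is analysed as one sample, a simplification of the two-visit model.

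- Imputed mean = (1 − m) × d.
- SE on observed data = 1/√(N(1 − m)).
- SE after imputation ≈ √((1 − m)(1 + m d²)/N).
- SE ratio ≈ (1 − m) × √(1 + m d²).

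The documents give no effect size for these variables. For illustration d is set to the TSH planning value, 0.7/1.9 = 0.368. For 9 of 47, m = 0.191: the estimate is multiplied by 1 − 0.191 = 0.809 and the SE by 0.809 × √(1 + 0.191 × 0.368²) = 0.809 × 1.013 = 0.819.

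Coverage and rejection rates come from 40,000 simulated datasets per row, shown as observed data / zero-imputed data.

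| Imputed | Estimate × | SE × | 95% CI coverage | Rejection at 0.05 |
|---|---|---|---|---|
| 2 of 47 | 0.957 | 0.960 | 95.1% / 95.0% | 67.9% / 67.9% |
| 5 of 47 | 0.894 | 0.900 | 94.9% / 94.1% | 64.9% / 64.8% |
| 9 of 47 | 0.809 | 0.819 | 95.0% / 91.8% | 60.0% / 60.0% |
| 12 of 60 | 0.800 | 0.811 | 95.0% / 90.7% | 70.9% / 70.9% |

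A larger change makes the undercoverage worse. At d = 0.5 with 9 of 47 imputed, the mean is 0.41 against 0.50, the interval width 0.54 against 0.65, and coverage 89% against 95%.

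**Where the shares come from.** SAP 4.1 reports 47 included and 45 completed, so 2 of 47 is the documented number of non-completers. 12 of 60 is the planned 20%, and 9 of 47 is close to it. 5 of 47 is an intermediate assumption. The number of dose-adjusted patients is not given. Because they remain in the study they can count as completers, so 2 is not an upper limit on the number imputed.

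**The case against.** The strongest reply has five parts.

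- **The rule need not produce a zero.** A reader might infer that LOCF can only impute zero change here. The documents do not support that: the attempted Final Visit in Protocol 7.4 collects every one of these tests, and an unscheduled visit may also yield a value. The SAP does not say whether an early-withdrawal sample is mapped to Visit 4, carried forward or ignored, nor whether a pre-treatment value may be carried into the treatment period. If it may not, nothing is imputed. This stands. It does not rescue dose-adjusted patients, whose later samples are excluded whenever they are taken.
- **Significance is not affected.** A reader might infer that a false finding of no change becomes easier to reach. Under the criterion in SAP 9.1 (two-tailed p below 0.05) it does not: mean and SE shrink almost equally, and the rejection rates agree to within 0.1 percentage point. This stands, under random missingness.
- **The unimputed run is already planned.** This limits the damage. However, the SAP ranks neither run, so the biased one could be reported as the main result.
- **Some cases are already covered.** The mITT set requires a valid Visit 3 TSH under the unchanged dose, so Visit 3 TSH is protected there. For lipids, SAP 9.4.2 names the panel as an endpoint but omits it from the modelled variables, so the interval argument applies to lipids only if they are modelled as in Protocol 11.3.6.
- **The original-data run is not a cure.** Dose-adjusted patients give it no Visit 4 value either, and with two time points it is close to an analysis of completers. This also stands.

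**Conclusion.** The concern holds as a bias in one of the two planned runs. For the ten variables at Visit 4 and the four at Visit 3, LOCF carries the tablet baseline forward unless a sample from before any dose change happens to exist. The estimated change and its interval then shrink by about the imputed share.

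The size is about 4% for the two documented non-completers, if neither had an early sample, with coverage essentially unchanged. It rises to 19–20% at the planned loss rate, with coverage of about 91–92% at 0.368 SD. A reader might take the upper figure as what happened in this study. The documents do not show that, because the number of dose-adjusted patients is not given.

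These results assume that values are missing at random and that baseline is what gets carried. If dose-adjusted patients had larger changes than the others, the attenuation would be greater. The variables are secondary in a study that calls itself a pilot, so this is a correction worth making rather than a threat to the primary result.

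**What to change.** In SAP 8 and 9.4.2:

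1. Limit LOCF to variables with an on-treatment value under the unchanged LT4 dose before the analysed visit, that is TSH, FT4, FT3 and TT3 at Visit 4.
2. For TT4, CPK, SHBG, ferritin, ACE, the lipids and all Visit 3 endpoints, name the planned original-data analysis as the lead.
3. If an imputed run is kept for those variables, label it a baseline-carried-forward sensitivity analysis.
4. State how early-withdrawal samples are mapped: to Visit 4, carried forward, or not used.

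The cost is a few sentences and possibly fewer tables; no new data are needed. The price is fewer patients and a wider interval for these variables. The original-data analysis still does not remove bias if the missing values of dose-adjusted patients are informative, so the report should give their number alongside these results.

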#### Partial dates imputation:

##### *Prior and Concomitant Medications*

Partial start dates will be computed as follow:

- If day is missing the first day of the reported month will be imputed.
- If month and day are missing the 1st January will be imputed.
- If month, day and year are missing no imputation will be applied.

Partial end dates will be computed as follow:

- If day is missing the last day of the reported month will be imputed.
- If month and day are missing the 31st December will be imputed.
- If month, day and year are missing no imputation will be applied.

Prior and concomitant medications without an end date will be considered as ongoing.

*Adverse Events*

Partial start dates will be computed as follow:

- If day is missing the first day of the reported month will be imputed.
- If month and day are missing the 1st January will be imputed.
- If month, day and year are missing no imputation will be applied.

Partial end dates will be computed as follow:

- If day is missing the last day of the reported month will be imputed.
- If month and day are missing the 31st December will be imputed.
- If month, day and year are missing no imputation will be applied.

Adverse events without an end date will be considered as ongoing.

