## **9.3 Safety variables**

Adverse events will be recorded at each visit. In addition, a physical examination including vital signs, neck exam, cardiac exam and respiratory exam will be performed at screening and final visits. Body weight will be recorded at screening, baseline and final visit.

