**Adverse Events Form (page 2/2)**

A.E. description	A.E. onset		A.E. stopped		Study Drug last admin. before AE		Seriousness 1-2	Severity 1-3	Action taken 1-7	Outcome 1-6	Relationship to treatment 1-6	Personnel Initials
	dd/mm/yyyy	hh mm	dd/mm/yyyy	hh mm	dd/mm/yyyy	hh mm						
1)												
2)												
3)												
4)												
5)												
ACTION TAKEN: if given as 2-7 please give details												
OUTCOME: if given as 2-6 please give details:												
RELATIONSHIP: if given as 5-6 please give details:												
SEVERITY: if given as 3 please give details:												

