**SAE(s) description**

Diagnosis(es)	Please complete in order of importance		
(if no diagnosis available give main symptoms)	1	2	3
.....	.....	.....	.....
.....	.....	.....	.....
.....	.....	.....	.....
Date and time of onset	...../...../..... day month year ..... hours min	...../...../..... day month year ..... hours min	...../...../..... day month year ..... hours min
Date and time ended	...../...../..... day month year ..... hours min	...../...../..... day month year ..... hours min	...../...../..... day month year ..... hours min
(tick continuing box if not ended)	 continuing	 continuing	 continuing
Severity / maximum intensity	 1. mild  2. moderate  3. severe	 1. mild  2. moderate  3. severe	 1. mild  2. moderate  3. severe
Study drug relationship	 1. certain  2. probable  3. possible  4. unlikely  5. not assessable  6. not related	 1. certain  2. probable  3. possible  4. unlikely  5. not assessable  6. not related	 1. certain  2. probable  3. possible  4. unlikely  5. not assessable  6. not related

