## **5 DEFINITIONS AND DATA CONVENTIONS**

### Age

Age will be calculated in decimal form as portion of the date of screening visit minus the date of birth, divided by 365.25 days per year, and then rounded down, that is:

$$\text{Age (years)} = \text{Floor}((\text{date of screening visit} - \text{date of birth}) / 365.25).$$

Body Mass Index (BMI)

BMI will be computed using the following formula:

$$\text{BMI} = \text{Body Weight (kg)} / (\text{Height (m)})^2$$

Daily dosage

Daily dosage (mcg) will be computed for each patient as:

$$\text{Daily Dosage} = \left( \frac{\sum_{i=1}^7 (\text{daily dosage}_i [\text{mcg}])}{7} \right)$$

where “i” is the day of the week.

Daily dosage/Body Weight

Daily dosage/Body Weight (mcg / kg) will be computed for each patient as:

$$\text{Daily Dosage/Body Weight} = \frac{\left( \frac{\sum_{i=1}^7 (\text{daily dosage}_i [\text{mcg}])}{7} \right)}{\text{Weight [kg]}}$$

where “i” is the day of the week.

Prior medications

Medications reported with an end date before the first study treatment administration (end date < date of first study treatment administration). As prior medication will be also indicated all medications reported by patients who didn't took the study treatment.

Concomitant medications

Medications reported as ongoing or with an end date after the first study treatment administration (ongoing or end date ≥ date of first study treatment administration).

Treatment-Emergent Adverse Events (TEAEs)

Adverse events who started after the start of the study treatment, adverse events without start date and with an end date after the start of the study treatment or adverse events without start date reported as ongoing (for patients who take at least one dose of study treatment).

Pre-Treatment Adverse Events (PTAEs)

Adverse events started after the subject's inclusion into the study but before the effective study treatment period (start date < date of first study treatment administration).

Serious Adverse Events (SAEs)

Adverse Event judged as serious.

Drug related Adverse Events

Adverse Events with a relationship to treatment reported as "Certain", "Probable" or "Possible".

Adverse events leading to discontinuation

Adverse Events leading to discontinuation is an AE with action taken equal to "Drug withdrawn".

Adverse events leading to death

Adverse Events leading to death is an AE with outcome equal to "Fatal".

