### 9.5.2 Adverse Events

Adverse events (AEs) intensity and frequency will be analysed during the pre-treatment phase and in the treatment phase until End of Study Visit.

The following summary tables will be provided:

- Adverse Events by SOC and PT;
- Serious Adverse Events by SOC and PT;

- Drug related Adverse Events by SOC and PT;
- Pre-Treatment Adverse Events by SOC and PT;
- Serious Pre-Treatment Adverse Events by SOC and PT;
- Treatment-Emergent Adverse Events by SOC and PT;
- Serious Treatment-Emergent Adverse Events by SOC and PT;
- Drug related Treatment-Emergent Adverse Events by SOC and PT;

Serious adverse events and fatal adverse events will also be listed.

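### Partial adverse-event start dates are imputed without reference to first dose, so an on-Tirosint event partially dated in the first-dose month or year leaves the TEAE tables

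*SAP*

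**What the plan says.** **Imputation (SAP section 8, Adverse Events).** For start dates, "If day is missing the first day of the reported month will be imputed". If the month is missing too, 1 January is used. If nothing is known, nothing is imputed. Partial end dates go to the last day of the month or to 31 December, and "Adverse events without an end date will be considered as ongoing". The start-date rule does not use the first-dose date, the end date or the ongoing status.

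**Classification (SAP section 5).** The TEAE definition begins "Adverse events who started after the start of the study treatment, adverse events without start date and with an end date after the start" of treatment, and adds undated events reported as ongoing in treated patients. Pre-treatment events are those with onset after inclusion but "before the effective study treatment period (start date < date of first study treatment administration".

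**Use (SAP section 9.5.2).** All AEs, pre-treatment AEs and TEAEs are tabulated separately. The TEAE set includes serious TEAEs and "Drug related Treatment-Emergent Adverse Events by SOC and PT".

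**Collection.** Protocol section 10 collects AEs from consent, and the run-in lasts 4 to 6 weeks, so events can arise on either side of first dose. Protocol section 9.3 states that "Adverse events will be recorded at each visit". The AE form in Protocol Appendix I asks for a full onset date and has a field headed "Study Drug last admin. before AE".

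**The concern.** An imputed start date is never later than the true one. The start-date rule can therefore move an on-treatment event to before first dose, but can never do the reverse. The events at risk are those in the calendar month of the switch from tablets to capsules.

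The plan also departs from its own caution. An ongoing event with no start date at all is a TEAE, but the same event with its month known can become pre-treatment.

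What is at stake is the completeness of the TEAE, serious TEAE and drug-related TEAE tables. Loss from the serious table is unlikely, because the SAE form asks for "Date and time of onset". The end-date rules can push events into the TEAE tables, but only events with no start date.

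**Working it through.** The plan gives no figure to reproduce, so the check applies the two rules together.

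**Example (illustrative dates).** First dose 12 March 2018, true onset after that day:

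| Recorded start | Imputed start | Class under SAP 5 |
|---|---|---|
| March 2018 | 1 March 2018 | before first dose, not a TEAE |
| 2018 | 1 January 2018 | before first dose, not a TEAE |
| April 2018 | 1 April 2018 | TEAE (correct) |
| nothing, ongoing | none | TEAE |

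If dosing began on the 1st, the imputed date equals the first-dose date. On the literal wording it is then neither before first dose nor after it.

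**Share misplaced when the day is missing.** Inputs: treatment of 84 days (77 to 91) from the study schedule. Assumptions: first dose equally likely on every day of 2017 to 2019, and onset equally likely on each day from first dose (day 0) to the end of treatment.

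- In a month of m days, the average number of on-treatment days left in the first-dose month, leaving out first doses on the 1st, is (m − 1)/2. That is 15 for 31-day months, 14.5 for 30-day months and 13.5 for February.
- Weighted by days in the year: (217 × 15 + 120 × 14.5 + 28 × 13.5)/365 = 5373/365 = 14.72 days.
- Share, onset days 0 to 84: 14.72/85 = 17.3%. Days 0 to 77: 14.72/78 = 18.9%. Days 0 to 91: 14.72/92 = 16.0%.
- Counting ties on the 1st as lost adds one day: 15.72/85 = 18.5% (20.2% and 17.1% at 77 and 91 days).
- Leaving out day 0 (onset days 1 to 84) gives 16.4% (17.9% to 15.1%).

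Enumeration over the calendar gives the same values. For year-only dates it gives 88%, but that pattern is unlikely in a 12-week study and is not carried forward.

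**Events lost.** The documents give neither the number of TEAEs nor the rate of partial dates, so both are assumed. Events lost = TEAEs × proportion with day missing × 0.173:

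- 25 × 1% × 0.173 = 0.04
- 50 × 10% × 0.173 = 0.87
- 75 × 20% × 0.173 = 2.6 (with ties, × 0.185 = 2.8)

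**Reverse error if the first-dose date is imputed instead.** This is the share of run-in events with a missing day that fall in the month of first dose and would be counted as TEAEs. The 28- and 42-day run-ins come from the schedule; the event durations are assumed.

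| Check applied | 28-day run-in | 42-day run-in |
|---|---|---|
| None | 52% | 35% |
| Complete end date, 3-day event | 6.8% | 4.5% |
| Complete end date, 7-day event | 19.0% | 12.6% |
| Complete end date, 14-day event | 35.7% | 23.8% |

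**The case against.** **It may never happen.** The AE form asks for day, month, year and time. AEs are taken at each visit, Protocol section 11.1.2 provides queries and completeness checks, and Protocol section 12.1 provides source data verification. SAP section 4.1 reports only 47 patients in the treatment phase. All of this stands: the count is unknown and may be zero, and the range of events lost rests on assumptions.

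**Nothing disappears from the report.** Affected events remain in the overall AE, SAE and drug-related AE tables, and serious and fatal events are also listed. The study is single-arm and efficacy does not depend on the split. This stands and is why the point is minor.

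**The two errors are symmetrical.** Counted in onset days per patient, the current rule misplaces about 14.7 on-treatment days. Imputing first dose with no further check misplaces about 14.7 run-in days. This is correct. The gain comes from the end-date check, which cuts the reverse error to 1.9 days for 3-day events, 5.3 for 7-day events and 10.0 for 14-day events, but does nothing for ongoing events. For those, the choice is one of direction, and SAP section 5 already chooses over-counting for undated events.

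**The remedy has loose ends.** If only the imputed tie counts as a TEAE, a fully dated event on the day of first dose stays ambiguous. For year-only dates the unchecked reverse error is 94% to 96%. The form field on last drug intake is tied to onset and may be unreliable when the onset day is unknown. These are fair refinements. None rescues the current rule.

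**Conclusion.** The concern holds as a reading of the rules: sections 5 and 8 of the SAP together misplace on-treatment events partially dated in the month or year of first dose, and nothing elsewhere in the SAP or protocol overrides this. Partial dates in a later month or year are classed correctly.

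For events with the day missing, the misplaced share is about 17% (16% to 19%), or 18.5% (17% to 20%) with ties, assuming uniform onset and uniform first-dose dates. The number of events is unknown: 0.04 to 2.6 (2.8 with ties) under the assumed counts, and possibly none. Severity is minor, because only the TEAE breakdown is affected.

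**What to change.** In SAP section 8, change the AE start-date rule. If the known month and year (or the year alone) equal those of first dose and the end date is not before first dose, impute the first-dose date and count the event as a TEAE. Where the form field "Study Drug last admin. before AE" shows whether Tirosint had already been taken, let that field decide. Otherwise keep the current rule.

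In SAP section 5, state that a TEAE starts on or after first dose, so that fully and partially dated events on that day are treated alike. As wording clean-up only, align the pre-treatment definition with its bracketed cut-off: it starts at inclusion, which the schedule places at Visit 2, so read literally it omits run-in events. Onset from consent to before first dose would match Protocol section 10; the SAE guidance in Appendix I, which starts collection at screening, should be reconciled with it.

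The cost is a few lines of SAP text and programming, with no new data. The price is the reverse error shown above. The end-date check does not help when the end date is missing, or is partial in the same month, because the event is then treated as ongoing or as ending at month end. In those cases the form field has to settle it. Reporting how many partial start dates fell in the first-dose month or year, and how each was classed, would show whether the rule mattered.
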